#### 3.6.2 Secondary (Supportive) Endpoints

The secondary endpoints are:

- a) Proportion of patients with mUFC  $\leq$  ULN at weeks 24, 36 and every 12 weeks until the earlier of loss to follow-up, death, or the end of the retrospective follow-up period or treatment.
- b) Change from baseline for biochemical variables to Week 4, 8, 12, 18, 24, 36, and to every 12 weeks until the earlier of loss to follow-up, death, or the end of the retrospective follow-up period or treatment.
- c) Actual and percent Change in BMI, ECG, blood pressure, metabolic, biochemical, and hormone levels from baseline for clinical outcomes to Week 4, 8, 12, 18, 24, 36, and to every 12 weeks until the earlier of loss to follow-up, death, or the end of the retrospective follow-up period or treatment discontinuation
- d) Change from initial dose.
- e) Proportion of participants who experienced TEAE and AESI

Project Document Version No.: 4.0; Document Effective Date: 30 October 2023

CONFIDENTIAL

- f) Change from baseline of measures of cortisol levels (mUFC, salivary cortisol and morning serum cortisol expressed as x-fold the ULN) to Week 4, 8, 12, 18, 24, 36, and to every 12 weeks until the earlier of loss to follow-up, death, or the end of the retrospective follow-up period or treatment.
- g) Partial responders (defined as patients with a ≥50% reduction from baseline, but still >ULN) for measures of cortisol levels (mUFC, salivary cortisol and morning serum and a combination of the 3 measures) to Week 4, 8, 12, 18, 24, 36, and to every 12 weeks until the earlier of loss to follow-up, death, or the end of the retrospective follow-up period or treatment discontinuation.
- h) Complete or partial responders: Proportion of participants with normalization of cortisol levels or a partial response: for cortisol levels (mUFC, salivary cortisol and morning serum and combination of the 3 measures) to Week 4, 8, 12, 18, 24, 36, and to every 12 weeks until the earlier of loss to follow-up, death, or the end of the retrospective follow-up period or treatment discontinuation.
- Composite of normalization cortisol measures at week 12: Patients with W12 mUFC ≤ ULN, or W 12 salivary cortisol ≤ ULN (if w12 mUFC is missing), or W 12 serum cortisol ≤ ULN (if W12 mUFC and salivary cortisol are missing)

# 3.6.3 Exploratory endpoint(s)

The exploratory effectiveness endpoint is:

- a) Proportion of participants with normal late night salivary cortisol at Week 4, 8, 12, 18, 24, 36, and at every 12 weeks until the earlier of loss to follow-up, death, or the end of the retrospective follow-up period or treatment discontinuation
- b) On-treatment analysis of cortisol levels
  - a. Normalization of cortisol measures at Week 4, 8, 12, 18, 24, 36, and at every 12 weeks until the earlier of loss to follow-up, death, or the end of the retrospective follow-up period or treatment discontinuation (mUFC, salivary cortisol and serum cortisol and a combination of the 3 measures). Participants with normal values at baseline would not enter in this analisis.
  - b. Composite of normalization of week 12 cortisol measures: For patients taking Osilodrostat on week 12 (mUFC, salivary cortisol and morning serum and a combination of the 3 measures).
  - c. Normalization to the last on treatment cortisol measures (mUFC, salivary cortisol and morning serum and a combination of the 3 measures).
  - d. Patients with normalization of the majority of cortisol measures: Defined as patients on Osilodrostat treatment that have multiple measures of cortisol levels over time and have >50% of these measures ≤ ULN (mUFC, salivary cortisol and morning serum and a combination of the 3 measures).
  - e. Change from baseline of measures cortisol level: Defined as the change from baseline in measures of cortisol levels including only patients receiving Osilodrostat the time-point (expressed by the unit and bx nfold ULN) for mUFC, salivary cortisol and morning serum and a combination of the 3 measures.
  - f. Complete or partial responders: The proportion of patients with normalization of cortisol levels or a ≥50% reduction from baseline for patients receiving Osilodrostat at week 4, 8, 12, 18, 24, 36, and at every 12 weeks until the earlier of loss to follow-up, death, or the end of the retrospective follow-up period or treatment discontinuation (mUFC, salivary cortisol and morning serum and a combination of the 3 measures).
  - g. Waterfall plot figures of change in measures of cortisol level from baseline to last on treatment expressed as n-fold ULN (mUFC, salivary cortisol and morning serum and a combination of the 3 measures) grouped by duration of exposure to osilodrostat (0 to 4 weeks, 5 to 8 weeks, 9 to 12 weeks, 13 to 24 weeks, >24 weeks).

Project Document Version No.: 4.0; Document Effective Date: 30 October 2023

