#### 5.3.3.6 Partial responder

A partial responder is defined as a participant with 50% reduction from baseline, but still >ULN for measures of cortisol levels.

The number and proportion of partial responders at Week 4, 8, 12, 18, 24, 36, and to every 12 weeks thereafter will be summarized descriptively along with associated 95% CI.

This will be reported for mUFC, salivary cortisol and morning serum cortisol as well as the combination of the 3 measures (any of the measures and reported as "Cortisol").

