#### 5.3.3.9 Composite normalization

The definition of composite normalization is the condition of the value  $\leq$  ULN of any type of cortisol. For any given time point a responder in this composite will be defined a patients with mUFC  $\leq$  ULN, or salivary cortisol  $\leq$  ULN (if mUFC is missing), or serum cortisol  $\leq$  ULN (if mUFC and salivary cortisol are missing).

The number and proportion of participant achieving composite normalization at 4, 8, 12, 24, 36 and every 12 weeks thereafter will be summarized descriptively along with associated 95% CI.

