#### 5.3.3.10 Time to normalization

Time to normalization is the interval between start of osilodrostat administration and time of normalization of cortisol levels.

Project Document Version No.: 4.0; Document Effective Date: 30 October 2023

CONFIDENTIAL

RECORDATI AG, Rare Diseases Branch LCI699-RECAG-NI-0596

Statistical Analysis Plan

The participants not reaching the normalization will be censored at the date of the last available cortisol measure.

In the case of the composite analysis the baseline would be the closest measure to the start of osilodrostat among the different cortisol assessments (mUFC, salivary and serum) and the time of normalization is the first occurring among the cortisol measures. Censored dates will be the date of the last available cortisol measure. In case of multiple measures at a timepoint the the definition of composite normalization will be applied.

This will be reported for mUFC, salivary cortisol and morning serum cortisol as well as the combination of the 3 measures (any of the measures and reported as "Cortisol").

The number and proportion of events and censored values will be presented together with median time, (95% CI), quartiles, minimum and maximum and Kaplan-Meier curves will be produced for analysis.

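### The combined cortisol change and waterfall outputs have no common scale and no same-analyte rule, and composite time to normalization can pair one analyte's baseline with another's event

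*SAP*

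**What the plan says.** Three groups of SAP outputs use a combination of mUFC, salivary cortisol and morning serum cortisol.

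- **Change and waterfall (3.6.3, b.e and b.g, exploratory).** Change from baseline is "expressed by the unit and bx nfold ULN) for mUFC, salivary cortisol and morning serum and a combination of the 3 measures". The waterfall plot shows change to the last on-treatment value, as n-fold ULN, for the same set. Section 5.3.4, which covers exploratory analysis, describes only late-night salivary cortisol and does not say how the combination is built.
- **Partial and complete-or-partial response (3.6.2 g and h, 3.6.3 b.f, 5.3.3.6, 5.3.3.7).** Section 5.3.3.6 states: "A partial responder is defined as a participant with 50% reduction from baseline, but still >ULN for measures of cortisol levels". It reports this for each analyte "as well as the combination of the 3 measures (any of the measures and reported as" Cortisol, and 5.3.3.7 uses the same wording. Neither section says which baseline the combination uses.
- **Composite time to normalization (5.3.3.10).** Here a baseline is given: "In the case of the composite analysis the baseline would be the closest measure to the start of osilodrostat among the different cortisol assessments". The event follows: "the time of normalization is the first occurring among the cortisol measures". Where several measures exist at one timepoint, the hierarchy of 5.3.3.9 applies: mUFC first, then salivary cortisol "ULN (if mUFC is missing), or serum cortisol" when both of the others are absent.

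The general baseline definition in 5.2 allows a value up to 2 weeks before initiation, and its missing-baseline rule is worded per variable. Footnote f to SAP Table 1 allows 1 month for mUFC.

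**The concern.** A change score or percent reduction means something only if both values measure the same quantity. A pooled change in units across a urinary measure, a salivary level and a serum level estimates nothing. Dividing by the ULN removes the unit, but it does not make the analytes interchangeable unless a patient sits at the same multiple of ULN on all three. The documents do not claim this.

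If the analyte may differ between baseline and follow-up, a patient with no change in any analyte can appear to improve, and a patient with a real fall can appear to worsen. In the time-to-event analysis, an analyte that was never abnormal can supply the normalization event. The study is intended to support an FDA supplemental application, and SAP 5.10 repeats the composite cortisol response by subgroup, so such errors would reach more than one table.

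**Working it through.** The plan gives no figure to reproduce: these endpoints are descriptive, and neither document gives cortisol values by analyte. All values below are assumptions chosen to show the mechanism.

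**1. Is there a common scale?** For b.e in units, no. For b.e and b.g in n-fold ULN, only if baseline and follow-up come from one analyte. No section of either document requires that.

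**2. Single patients.** Let baseline be *a*×ULN on analyte A and the later value *b*×ULN on analyte B. Apparent change = *b*/*a* − 1.

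- False reduction: baseline mUFC 10, later serum 1.2, serum unchanged throughout. 1.2/10 − 1 = −88%. The value is still above ULN, so it would meet partial response. Within serum, 1.2/1.2 − 1 = 0%.
- Hidden reduction: baseline serum 1.3, later mUFC 4, where mUFC started at 10. 4/1.3 − 1 = +208%. Within mUFC, 4/10 − 1 = −60%, a partial response.

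**3. How often, among mismatched pairs with no true change?** Let ln(*b*/*a*) be normal with mean ln *m* and SD *s*, where *m* is the median ratio of the two analytes in n-fold ULN. Then P(apparent fall ≥50%) = Φ[(ln 0.5 − ln *m*)/*s*].

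| *m* | *s* = 0.3 | *s* = 0.5 | *s* = 0.8 |
|---|---|---|---|
| 1.0 | 1.0% | 8.3% | 19.3% |
| 0.75 | 8.8% | 20.9% | 30.6% |
| 0.5 | 50% | 50% | 50% |

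For a same-analyte pair *m* = 1, and the figure is 0.03%, 1.0%, 4.2% or 8.3% for *s* of 0.2, 0.3, 0.4 or 0.5. The excess from mixing analytes therefore comes from unequal n-fold levels (*m* below 1) or a wider spread. It does not come from switching as such.

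**4. Patients affected.** If 10% to 30% of 100 stable patients had mismatched pairs, apparent falls of at least 50% would number 100 × 0.10 × 0.083 = 0.8 to 100 × 0.30 × 0.083 = 2.5 at *m* = 1, *s* = 0.5. At *m* = 0.5 they would number 100 × 0.10 × 0.5 = 5 to 100 × 0.30 × 0.5 = 15.

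**5. Time to normalization.** Suppose baseline mUFC is 10×ULN and closest to treatment start, serum is 0.9×ULN throughout, and only serum is available at the first visit. The hierarchy falls through to serum, 0.9 ≤ 1, and the patient is recorded as normalized at that visit with nothing changed. If mUFC had been measured at that visit it would have taken precedence, so the error needs missing mUFC and salivary values at the visit.

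**6. Does the closest-measure rule favour one analyte?** It can. A baseline mUFC may be up to 1 month old under footnote f, while the other analytes fall within 2 weeks, so serum or salivary cortisol may be the closer measure even when a baseline mUFC exists.

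**The case against.** A reader might infer that every combined endpoint takes its baseline from the closest of the three analytes and its follow-up from the mUFC, salivary, serum hierarchy. The documents do not support that. The closest-measure rule appears only in 5.3.3.10, where no change or percent reduction is calculated. The hierarchy is written for composite normalization. Neither is attached to change, waterfall or partial response.

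For the responder endpoints, the any-measure wording can fairly be read as a response within any one analyte, and the per-variable wording in 5.2 is consistent with that. On this reading the first patient above is not a partial responder, the second is, and both responder errors disappear. This stands as an available reading, but it is not written down. It also allows three chances to respond: an assumed 5% false response on each analyte becomes up to 1 − 0.95³ = 14.3% if they are independent. And it cannot rescue b.e or b.g, which need one change value per patient.

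A reader might also infer that all the combined outputs are meant to stand in for missing mUFC. That fallback is written only for composite normalization, which uses no percent change.

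The remaining objections limit the consequence and are accepted. The study is descriptive, and each combined output sits beside its three analyte-specific versions. Secondary endpoint f and 5.3.3.3 report n-fold change by analyte with no combination. Item b.a of 3.6.3 drops patients with normal baseline values, but that is stated only for on-treatment normalization, and without saying which analyte decides it for the combination.

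**Conclusion.** The concern holds in limited form. The combined change in units has no meaning under any reading. The combined n-fold change and waterfall are undefined and permit cross-analyte comparison. The rule written in 5.3.3.10 can pair an abnormal baseline on one analyte with a normalization event on another that was normal throughout. For combined partial and complete-or-partial response the fault is an undefined baseline: a cross-analyte reading could create or hide a reduction of at least 50%, but the SAP does not prescribe it.

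The size cannot be established from the documents. The −88% and +208% cases and the counts of 0.8 to 15 per 100 rest on assumed analyte ratios, spreads and mismatch shares. That a patient can be far above ULN on mUFC and near it on serum is likewise an assumption. The affected outputs are secondary or exploratory. The primary endpoint, mUFC at or below ULN at 12 weeks, uses none of these rules. The SAP should be corrected, but the main result does not depend on it.

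**What to change.** 1. In 3.6.3 b.e and b.g, strike the combination of the three measures and keep the three analyte-specific outputs, which are already planned.
2. In 3.6.2 g and h, 3.6.3 b.f, 5.3.3.6 and 5.3.3.7, state that the reduction of at least 50% is always computed from baseline and visit values of the same analyte, before any combination. Report how many patients contribute each analyte.
3. In 5.3.3.10, count a composite normalization event only on an analyte that was above ULN at its own baseline. The patient in step 5 of the working would then stay at risk until an analyte that was abnormal at baseline normalizes, or be censored.

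The cost is SAP wording and a small programming change. The downside is that fewer patients will be evaluable for the combined endpoints, and their rates may be lower. Removing the combined change and waterfall loses no interpretable result.

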**CONFIDENTIAL** 

#### 4 DATA SOURCE

The primary data source for this study will be the existing electronic medical records stored in the hospital information management systems (HIMS) and laboratory information management systems (LIMS) at the investigative sites. Also, where applicable, data will be captured from paper medical records. The Investigator or authorized medical staff will record clinical and treatment data from participants' medical files into the eCRF.

#### Participant identification period:

Participants meeting eligibility criteria will be retrospectively identified and included in the study by site investigators based on a review of medical records at site. Site policies and local regulations regarding participant consent (NOL) will be followed. All eligible participants identified at a site between April 2019 and study start date and consenting to be part of the study will be included.

#### Index date:

The index date is the first dose of osilodrostat (index treatment).

#### 5 STATISTICAL METHODS

#### 5.1 Data Quality Assurance

All tables, figures, and data listings to be included in the report will be independently checked for consistency, integrity and in accordance with standard PAREXEL procedures for analysis and reporting.

The data for the planned analysis will be quality controlled as per applicable PAREXEL standard operating procedures. The data extraction will be set to an appropriate date so that all data cleaning activities which include any corrections are taken care of.

#### 5.2 General Presentation Considerations

All report outputs will be produced using SAS® version 9.4 or a later version in a secure and validated environment. All report outputs will be provided to the Sponsor in a single Microsoft Word document. Medical history, procedural/surgical history, and Adverse Events (AE) will be coded using the current version of the Medical Dictionary for Regulatory Activities (MedDRA). The frequency count and percentage of participants will be summarized according to the coded terms of system organ class (SOC) and preferred term. Participant-wise data listing will be provided.

Using the World Health Organization Drug Dictionary (WHO DD), prior and concomitant medications will be tabulated by drug classification, preferred drug name and study group.

Continuous data will be summarized in terms of the descriptive statistics, number of observations (n), mean and SE of mean or 95% CI of mean (as appropriate), SD, median and associated 95% CI of median (as appropriate), minimum, and maximum, unless otherwise stated.

Continuous data that are expected to be skewed and will be presented in terms of the maximum, upper quartile, median, lower quartile, minimum and number of observations. The mean, median will be reported to one more decimal place than the raw data recorded in the database. The SD will be reported to two more decimal places than the raw data recorded in the database. In general, the maximum number of decimal places reported shall be four for any summary statistic.

Project Document Version No.: 4.0; Document Effective Date: 30 October 2023

CONFIDENTIAL

Page 18 of 31

TP-GDO-WW-096-09 Effective Date: 22 Dec 21

Related to: SOP-GDO-WW-019

Categorical data will be summarized in terms of the number of participants providing data at the relevant time point (N), frequency counts and percentages.

Time to event endpoints will be summarized in terms of participants providing data, median and quartiles and represented graphically by Kaplan-Meier curves.

Percentages will be presented to one decimal place. Percentages will not be presented for zero counts. Percentages will be calculated using N as the denominator.

Changes from baseline in categorical data will be summarized using shift tables where appropriate.

Confidence intervals will be presented to one more decimal place than the raw data.

95% confidence intervals for proportions will be calculated using the exact (Clopper-Pearson) method, unless stated otherwise.

Baseline is defined as the available value at the time of osilodrostat initiation or the closest value within 2 weeks prior to osilodrostat initiation.

Change from baseline will be calculated as the post-baseline value of interest minus the baseline value. Percent change from baseline is defined as:  $100 \times [(post-baseline - baseline) / baseline]$ . If all baseline values are missing for a particular variable, the change from baseline and percent change from baseline will not be calculated.

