8.7 Data Analysis

Statistical analysis of this study will be the responsibility of the sponsor's designee.

Any change to the data analysis methods described in the protocol will require an amendment only if it changes a principal feature of the protocol. Any other change to the data analysis methods described in the protocol, and justification for making the change, will be described in the final statistical analysis plan (SAP). The SAP will be developed as a separate document and approved prior to database lock, containing a description of the planned statistical analysis in detail with Tables, Figures and Listings (TFLs) templates.

Any deviations from the planned analyses will be described and justified in the final study report.

The overview of statistical analysis is detailed in the below section.

Final v2.0 47 of 63 18 April 2023

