8.7.2 General Considerations

An SAP describing the planned statistical analysis in detail with TLF templates will be developed as a separate document. All statistical analyses will be performed using Statistical Analysis System® (version 9.4 or higher) unless otherwise stated.

No formal statistical hypothesis testing will be performed, and all the analyses will be primarily descriptive in nature. When appropriate, and unless otherwise specified, 95% confidence intervals (CIs) will be displayed.

Descriptive statistics will include the number of available data, number of missing data and the following:

- Mean and associated standard error of mean (SE) standard deviation (SD), minimum, median, maximum, first and third quartiles and 95% CIs for means/medians, minimum (Min), maximum (Max).
- Counts and percentages of each category for categorical variables with 95% CIs.

Percentages will be based on the number of patients in safety or ITT population.

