8.7.3 Analysis Population(s)

The ITT population consists of all enrolled participants who, have met all inclusion/exclusion criteria and have received osilodrostat treatment for non-CD CS, with a potential follow-up of at least 12 weeks. The only patients excluded from the primary efficacy analyses will be the ones who started treatment with osilodrostat less than 12 weeks prior to the end of the abstraction period, and are still treated with osilodrostat at the end of the abstraction period. These patients will be included only in the analyses of the secondary and exploratory endpoints including safety.

Final v2.0 48 of 63 18 April 2023

The Safety population consists of all participants who receive at least one dose of osilodrostat.

All effectiveness analysis will be performed on ITT population. Safety analysis will be performed on the safety population.

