## 3.3 Primary Analysis Population

#### **ITT Population**

The Intent-to-treat population (ITT) consists of all enrolled participants who, have met all inclusion/exclusion criteria and have received osilodrostat treatment for non-CD CS, with a potential follow-up of at least 12 weeks. The only patients excluded from the primary efficacy analyses will be the ones who started treatment with osilodrostat less than 12 weeks prior to the end of the abstraction period and are still treated with osilodrostat at the end of the abstraction period. These patients will be included only in the analyses of the secondary and exploratory endpoints including safety.

All effectiveness analysis will be performed on the ITT population.

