#### 5.13 CHANGES FROM PROTOCOL

Currently the SAP elaborates analyses as planned in the protocol and some related analysis in addition to protocol specified analysis. This section is kept for documenting any changes made to the planned analyses in the study protocol due to various circumstances for e.g., a protocol amendment. Any such changes (if occurs) will be documented, and this section of SAP will be updated with all necessary details related to the change.

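### SAP 5.2 divides by patients with data, while Protocol 8.7.2 divides by the ITT or safety population: no text says which governs the Week-12 response rate or how on-treatment patients without a Week-12 mUFC count

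*SAP*

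**What the plan says.** **Protocol.** Section 8.7.2 states: "Percentages will be based on the number of patients in safety or ITT population". Section 8.7.3 adds: "All effectiveness analysis will be performed on ITT population". Section 8.7 deals with analysis changes too small for an amendment: "Any other change to the data analysis methods described in the protocol, and justification for making the change, will be described in the final". The document meant there is the SAP.

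**SAP, general rule.** Section 5.2 has categorical data "summarized in terms of the number of participants providing data at the relevant time point (N), frequency counts and percentages", and then: "Percentages will be calculated using N as the denominator".

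**SAP, population rule.** Section 3.3 states: "All effectiveness analysis will be performed on the ITT population". It allows one exclusion: "The only patients excluded from the primary efficacy analyses will be the ones who started treatment with osilodrostat less than 12 weeks prior". The reference point is the close of abstraction, and the patient must still be on treatment then. A separate modified ITT (mITT) then removes patients without a Week-12 mUFC, unless the reason was safety.

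**SAP, endpoint rules.** Section 5.3.2 makes non-responders of patients who stopped before Week 12 or were lost to follow-up. It names no denominator. Section 5.3.3.1 gives neither a denominator nor a non-responder rule for Week 24 onward. Section 5.11.1 does not replace missing data for primary or secondary endpoints.

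**SAP, change log.** Section 5.13 reads: "Currently the SAP elaborates analyses as planned in the protocol and some related analysis in addition to protocol specified analysis". It lists no change of denominator, and neither does the revision history.

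**The concern.** The primary endpoint is a proportion at one time point, so the categorical-data rule in SAP 5.2 covers it on its face. That rule and Protocol 8.7.2 give different denominators whenever a patient is still on treatment but has no in-window Week-12 mUFC. Such patients are to be expected: values come from routine care and are collected only where available, and the SAP sets up a five-step review of missing Week-12 mUFC.

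The study has a single arm and is meant to support a label expansion, so the Week-12 proportion is its main effectiveness result. Two programmers following the SAP could report different primary percentages from the same data. The choice also affects the only robustness check. SAP 5.3.5 plans no formal sensitivity analysis and relies on repeating the primary analysis in the mITT and On-Treatment populations. If 5.2 governs the ITT run, that run loses the same unmeasured on-treatment patients that the mITT removes, and the contrast between the two is weakened.

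**Working it through.** **1. Who is affected at Week 12.**
- Stopped before Week 12, or lost: non-responders (Protocol 8.7.8, SAP 5.3.2). The denominator conflict does not touch them.
- Started less than 12 weeks before the end of abstraction and still treated: excluded (SAP 3.3).
- On treatment with an in-window mUFC: classified by the value.
- On treatment with no in-window mUFC: no sentence classifies them. Call their number m.

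**2. What each text does with those m patients.**
- Protocol 8.7.2 and 8.7.3: they are in the denominator and cannot be in the numerator, so they count as not responding by arithmetic, although no rule says so.
- SAP 3.3: they are not the one permitted exclusion, and they are removed only to form the mITT, so the ITT contains them.
- SAP 5.2 with 5.11.1: they provide no data and nothing is replaced, so they leave N.
- For adverse events, SAP 5.9.1 restates a denominator (the safety population). Section 5.3.2 has no matching sentence for the primary endpoint.

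**3. Check of the interval method.** The plan derives no figure for this endpoint. The exact (Clopper-Pearson) method named in SAP 5.2 was checked on the LINC 3 result in Protocol section 6: 93/137 = 67.9%, 95% CI 59.37 to 75.60, as printed there.

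**4. Size at Week 12.** With x responders among N ITT patients, the ITT rate is x/N and the literal 5.2 rate is x/(N−m). Their ratio is N/(N−m), which is never below 1. N=100 follows the planned size of about 100; x and m are assumed, because the documents give neither.

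| x | m | ITT denominator | SAP 5.2 denominator |
|---|---|---|---|
| 50 | 5 | 50.0% (39.8–60.2) | 50/95 = 52.6% (42.1–63.0) |
| 50 | 10 | 50.0% (39.8–60.2) | 50/90 = 55.6% (44.7–66.0) |
| 50 | 20 | 50.0% (39.8–60.2) | 50/80 = 62.5% (51.0–73.1) |
| 30 | 10 | 30.0% (21.2–40.0) | 30/90 = 33.3% (23.7–44.1) |
| 70 | 10 | 70.0% | 70/90 = 77.8% (67.8–85.9) |

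With m=0 the two rules agree.

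**5. Week 24 onward.** Protocol 8.7.2 and 8.7.3 give the ITT; SAP 5.2 gives patients with data. This is the same conflict, now without any non-responder rule. Assume 50/80 = 62.5% controlled at Week 12, 12 patients leaving, and nobody else changing status:

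| Controlled leavers | Uncontrolled leavers | Patients with data | All 80 |
|---|---|---|---|
| 2 | 10 | 48/68 = 70.6% (58.3–81.0) | 48/80 = 60.0% |
| 8 | 4 | 42/68 = 61.8% (49.2–73.3) | 42/80 = 52.5% |
| 10 | 2 | 40/68 = 58.8% (46.2–70.6) | 40/80 = 50.0% |

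The observed-case figure can rise or fall from 62.5% through attrition alone.

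The full ITT is not automatically the right later denominator either. It requires only 12 weeks of potential follow-up, and a patient starting on 16 December 2022 reaches Week 12 on 10 March 2023, Week 24 on 2 June 2023 and Week 36 on 25 August 2023. The text reviewed does not give the end-of-abstraction date.

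**6. A secondary dependence.** The Week-12 window is 12 ± 4, that is Weeks 8 to 16. A normal value from Weeks 8 to 12 may belong to a patient who stopped before Week 12 and is therefore a non-responder. That call needs an end-of-treatment date, and SAP 5.9.5 says these are often missing. Section 5.3.2 cites none of the SAP's date rules. At N=100, each patient reassigned in this way moves the rate by 1 point.

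**The case against.** The strongest reply is that 5.2 is general presentation text, whereas SAP 3.3 is specific: it permits one exclusion from the primary analysis and builds a separate mITT to remove unmeasured patients. On that reading the ITT denominator holds, nothing has changed from the protocol, and there is nothing to log. This is the better reading, and it rules out saying that the SAP will drop these patients or will inflate the primary rate. It does not close the point. Membership of the ITT does not by itself set a percentage denominator, and no sentence gives 3.3 precedence over 5.2 or says how an unmeasured patient counts.

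A reader might also infer that neither document gives a denominator from Week 24. They do: the general rules in Protocol 8.7.2 and 8.7.3 and in SAP 5.2 reach those visits. What both lack there is a non-responder rule. Nor is the reader wholly uninformed. The endpoint text in SAP 3.6.2 ends with follow-up or treatment, N is reported at each time point, Protocol 8.7.2 asks for the number missing, and SAP 5.3.2 provides a patient listing.

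The SAP does handle part of the problem. Reasons for each missing Week-12 mUFC are traced, exclusions are decided and documented before database lock, and 5.11.1 allows a decision before lock for a subject with many missing values. These are case-by-case decisions, not a denominator rule.

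It is tempting to count three competing end-of-treatment rules. The On-Treatment rule in 3.3 and approach A in 5.9.5 use the same end-of-study reasons and the same handling of a change to 0 mg, so in substance there are two. Approach B differs for other end-of-study reasons. Loss to follow-up would be one of these, and 5.3.2 already makes lost patients non-responders. The issue is therefore secondary.

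Finally, the sizes are assumed, the primary endpoint has no success threshold, and the 52.6% and 55.6% examples lie inside the ITT interval of 39.8 to 60.2. That limits the size that can be claimed, but it does not resolve the conflict between the texts.

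**Conclusion.** The point holds as an unresolved conflict of denominators and should be fixed. At Week 12, SAP 5.2 applied literally contradicts Protocol 8.7.2 and SAP 3.3, and it can only leave the response rate unchanged or raise it, by the factor N/(N−m). With N=100 and 50 responders, the assumed values m=5, 10 and 20 add 2.6, 5.6 and 12.5 points. The documents give no missingness rate, so the actual effect is unknown and is zero if m=0.

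From Week 24 the same conflict applies with no non-responder rule. The 5.2 result there is an observed-case proportion, and the documents do not fix which way it is biased; an upward bias should not be assumed. The missing entry in 5.13 is a failure to record a change only if 5.2 is meant to govern. If 3.3 governs, what is missing is one clarifying sentence.

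**What to change.** (a) In SAP 5.3.2, state that the Week-12 denominator is the full ITT after the one exclusion permitted in 3.3. Count on-treatment patients with no in-window mUFC as non-responders, and show the observed-case percentage beside it. Limit the rule in 5.2 to other summaries, and amend 5.11.1 so that its ban on replacing missing data does not contradict this classification.

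(b) In 5.3.3.1, label the proportions from Week 24 as observed-case while on treatment. Beside each, show the proportion among ITT patients whose potential follow-up reaches that visit, with the numbers discontinued, lost, dead and not measured.

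(c) Record any departure from Protocol 8.7.2, with its justification, in 5.13.

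Secondary: state in 5.3.2 which existing end-of-treatment date rule (3.3 together with approach A in 5.9.5, or approach B) identifies patients who stopped before Week 12.

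The cost is SAP wording and a few table columns, with no new data. The Week-12 figure becomes less favourable than the observed-case one, and it is conservative where routine care simply produced no value. That is the reason for showing both.
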